The number,Random,group appears in the software in the running program is the patient serial number that has been arranged before, the random number generated by the software, and the grouping after randomization. 0 is defined as control group (Control group), and 1 is defined as transcutaneous acupoint electrical stimulation group (TEAS group).

Open:

The specific method of operation is that participants know which group they will be assigned

to and what kind of treatment they will receive. According to the grouping of random tables generated by SPSS, a researcher will independently give corresponding treatment measures to the participant who has had signed the informed consent form, and cover up the screen of the electroacupuncture instrument. Another data collection researcher who does not know about the grouping records the vital signs and other complications of the participant. Finally, all the data will be saved, and after all the data are collected, the professional statistical researchers will deal with the data accordingly.

Clinical intervention program

(1) group

- transcutaneous acupoint electrical stimulation group (TEAS group): 15 minutes before anesthesia, begin to receive dense wave electrical stimulation with the frequency of 10/50Hz at bilateral Neiguan and Zusanli points, and last until 30 minutes after subarachnoid administration.
- Control group (Control group): 15 minutes before anesthesia, begin to connect the electrode at the same acupoint, but no electrical stimulation is given, the duration is the same as that of the TEAS group.

(2) selection of acupoints

- Neiguan (PC6): be located on the palmar side of the forearm, two inches above the transverse carpal stria, between the tendon of the palmar longus muscle and the tendon of the radial carpal flexor muscle.
- Zusanli (ST36): be located in the anterolateral leg, three inches under the calf nose point, a transverse finger (middle finger) from the anterior tibial crest.

(3) TEAS stimulation parameters

- frequency: 10/50Hz
- waveform: dense wave
- intensity: from low to high, adjust the stimulation intensity until the patient feels slight tingling, taking the maximum inductance that the patient can tolerate, no muscle convulsions, no discomfort as the standard, and record the final stimulation intensity.
- duration: 45 minutes

3. Research steps:

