Blood pressure (BP), electrocardiogram (ECG) and pulse oxygen saturation (SpO2) are measured routinely after participants included in the study entered the operating room. At the same time, the changes of cardiac function indexes such as stroke volume (SV), stroke index (SI), cardiac output (CO), cardiac index (CI), cardiac function index (CPI), systemic peripheral vascular resistance (TPR) and systemic peripheral vascular resistance index (TPRI) are monitored by impedance cardiac output measurement system. At the same time, the venous channel is established, and after the venous channel is established, the compound sodium chloride injection 10ml / kg is infused for 15 minutes to eliminate the hypotension caused by the lack of blood

volume. The blood pressure, heart rate and other hemodynamic parameters of the 5 minutes after the participants enter the room are recorded as basic values. According to the grouping situation, the participants are intervened to deal with 45 minutes. During anesthesia, the participants take the left lying position, routinely use No. 17 Tuohy needle for puncture, the puncture point is L3-4, and the No. 25 lumbar anesthesia needle is placed after reaching the epidural space. After confirming the cerebrospinal fluid outflow, the equal specific gravity local anesthetic solution is injected, the solution is 0.75% bupivacaine 2ml and cerebrospinal fluid 1ml mixture, the drug dose 2ml is injected, the injection time is 15 seconds, the lumbar anesthesia needle is pulled out, the No. 20 epidural catheter is placed, and 3-4cm is placed on the side of the head. In order to prevent the hypotension syndrome in supine position caused by uterine compression of inferior vena cava, the participants adjust the bed inclination to the left 15° ~20° immediately after supine position. The mask is given to inhale oxygen with a flow rate of 2~3L/min. The anesthesia level is determined by acupuncture along the midline of the left clavicle, and the upper limit of the sensory block plane is controlled between T6~T8 by adjusting the height of the operation bed. The other adjuvant drugs are consistent.

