After subarachnoid administration, the hemodynamic data of the participants are recorded in 30 minutes every 2 minutes. When hypotension occurs, ephedrine 5-10mg is given. If the blood pressure is still low after 2 minutes, ephedrine 5-10mg can be given again until the blood pressure recovers. Atropine 0.3mg is given intravenously when bradycardia occurred.

The incidence of hypotension, nausea, vomiting, dizziness, chest tightness and dyspnea in the participants in 30 minutes after subarachnoid administration are recorded.

24 hours after operation, the satisfaction of the participants are investigated.

4. Evaluation index

Main indicators:

- the incidence of hypotension during 30mintes after subarachnoid administration

Secondary indicators:

- specific changes of hemodynamic parameters during 30minutes after subarachnoid administration
- the usage of ephedrine during 30minutes after subarachnoid administration
- the incidence of nausea and vomiting during 30minutes after subarachnoid administration
- the incidence of dizziness chest tightness and dyspnea during 30minutes after subarachnoid administration

5. Follow-up content

The satisfaction of the participants will be evaluated by follow-up 24 hours after the participants' operation.

Note:

- definition of hypotension: intraoperative systolic blood pressure < 90mmHg or blood pressure decreased by more than 30% of basal blood pressure
- definition of sinus bradycardia: heart rate < 50 beats / min

- satisfaction score: scores range from 0 to 10, the higher the score, the higher the participants' satisfaction with anesthesia

6. Technical route

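### Reactions to the stimulation are foreseen but used only to eliminate women: no scheduled two-arm recording covers them, and symptom recording misses the first 15 of 45 stimulation minutes

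*Protocol*

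**What the plan says.** **Exposure.** Under Clinical intervention program, item (1), the TEAS arm is to start early: "15 minutes before anesthesia, begin to receive dense wave electrical stimulation with the frequency of 10/50Hz at bilateral Neiguan and Zusanli points". Stimulation is to "last until 30 minutes after subarachnoid administration", and item (3) gives "duration: 45 minutes". Controls wear electrodes at the same points for the same time, without current.

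**Foreseen reactions.** Broken, infected or allergic skin at the points is an exclusion. Item (3) sets the intensity by "taking the maximum inductance that the patient can tolerate, no muscle convulsions, no discomfort as the standard". The Elimination Criteria include an adverse reaction caused by TEAS at any time in the trial.

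**Scheduled recording.** Section 3 (Research steps) says: "After subarachnoid administration, the hemodynamic data of the participants are recorded in 30 minutes every 2 minutes". For symptoms it says: "The incidence of hypotension, nausea, vomiting, dizziness, chest tightness and dyspnea in the participants in 30 minutes after subarachnoid administration are recorded". The indicators in section 4 use the same half hour.

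**Later contact.** Section 5 (Follow-up content) says: "The satisfaction of the participants will be evaluated by follow-up 24 hours after the participants' operation". The notes that follow define this as a 0 to 10 score of satisfaction with the anaesthetic.

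**General recording.** The paragraph headed Open, in section 2, has a recorder who does not know the grouping note vital signs and other complications. It gives no list and no window.

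**The concern.** The recording window is timed from the spinal injection, which suits hypotension and the symptoms that accompany it. The exposure under test starts earlier, and its own foreseeable harms (skin reaction, discomfort, muscle response) are of a different kind. Followed exactly, the protocol would yield a count of post-injection symptoms by arm but no defined count of reactions to the device. The women known to have had such a reaction would be marked for elimination. A reduction in hypotension could then be reported with no matching statement of what the stimulation cost the women who received it.

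This is a matter of what is collected, when, and at which contact. An SAP can tabulate only what the protocol has had recorded, so the point is not one that a protocol would normally leave to it. Who stays in the hypotension comparison is a separate question and is not argued here.

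**Working it through.** **1. Exposure time (Clinical intervention program, items 1 and 3).**
- Before anaesthesia: 15 min. After the spinal injection: 30 min.
- 15 + 30 = 45 min, which reproduces the stated duration. The sum treats the start of anaesthesia and the injection as one moment, as the protocol's own total implies.

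**2. Exposure time with scheduled symptom recording (section 3).**
- Covered: 30 min from the injection.
- Not covered: 45 − 30 = 15 min, and 15/45 = 33%.
- The scheduled records before the injection are the baseline haemodynamic values, taken 5 minutes after room entry, and the intensity finally reached. Neither is a symptom record.

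**3. Content of the scheduled record.**
- Section 3 lists six items: hypotension, nausea, vomiting, dizziness, chest tightness and dyspnoea. Skin, electrode-site, muscle or discomfort reactions: 0 of 6.
- Section 4 has one main and four secondary indicators: hypotension; haemodynamic changes; ephedrine use; nausea and vomiting; dizziness, chest tightness and dyspnoea. Stimulation reactions: 0 of 5.
- The opening summary adds a fetal Apgar score, which is not a stimulation reaction either.

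**4. After the electrodes come off.**
- Stimulation and symptom recording stop together, 30 minutes after the injection.
- One contact remains, at 24 hours. Sections 3 and 5 both describe it as satisfaction only.

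**5. The two other places where a reaction could surface.**

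| Route | What it provides | What it lacks |
|---|---|---|
| Elimination Criteria | Staff must notice a TEAS reaction, with no half-hour limit | Definition, method of asking, reporting rule. It requires TEAS as the cause, so it cannot be met in controls, who receive no current |
| Recorder's general note of complications (section 2, Open) | An open-ended chance to write a reaction down | List, window, indicator |

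Neither route gives a count that can be compared between arms. Controls have electrodes at the same sites for the same time, so a site reaction could be counted in both arms if it were recorded without first judging its cause.

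**The case against.** The strongest reply is that the protocol does not leave these events unseen. The elimination criterion cannot be applied unless staff notice a reaction and attribute it, and it runs throughout the trial. The recorder may note other complications. Blood pressure, ECG, oxygen saturation and impedance indexes are monitored from room entry. Intensity is raised against the woman's own sensation before the block, so discomfort is under observation in just those first 15 minutes. The sentence in section 3 lists study outcomes timed from the injection and does not claim to be the whole harm schedule.

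Much of this stands. A reader might infer that reactions in the first 15 minutes, or at the electrode sites, go wholly uncollected, or that the trial could report no device harm. The documents do not support that: there are routes by which a reaction can be noticed and written down. The reply does not supply a definition, a schedule, a two-arm count or an indicator, and the clearer of the two routes leads to elimination of the woman.

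A reader might also infer that leg-site reactions are hidden by the block, since "the upper limit of the sensory block plane is controlled between T6~T8", and appear only once it wears off. That goes beyond the text. The protocol gives no block duration and describes no delayed electrode reaction. The forearm sites are a separate matter from the leg sites, and muscle convulsions can be seen without sensation. The point does not need this argument.

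The absence of 2-minute haemodynamic recording before the injection is likewise not the fault here. Monitoring is in place, and a denser pre-injection record would be a preference.

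**Conclusion.** The point holds as a gap in scheduled collection and reporting. One third of the stimulation time (15 of 45 minutes) lies outside the scheduled symptom window. No listed item or indicator names a stimulation or electrode-site reaction. The one later contact is described as satisfaction only. The protocol foresees these reactions and then gives them a single use, elimination.

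This is more than missing detail, because the protocol positively fixes a window and a follow-up content that do not cover the exposure. It is also limited: the hypotension comparison, its window and the sample size are untouched, and the protocol gives no figure for how often reactions occur, so the number of events at stake cannot be stated. It is a cheap improvement and no threat to the main result.

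The conclusion rests on two readings: that section 3 and section 4 fix what is scheduled, and that the general note of complications in section 2 adds no defined item to them. The case report form is not shown. If it already has lines for stimulation and site reactions from electrode connection onward in both arms, only the protocol wording needs to catch up.

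**What to change.** In section 3 (Research steps) and section 4 (Evaluation index):

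- Start recording symptoms, and any stimulation or electrode-site reaction, when the electrodes are connected, in both arms and whatever the presumed cause.
- Tabulate pre-injection events separately, so the primary window is unchanged.
- Note the state of all four electrode sites when the electrodes are removed.
- At the existing 24-hour contact, ask about stimulation and site reactions as well as satisfaction; amend section 5 to match.
- Add one indicator: such reactions from electrode connection to the 24-hour contact, by randomised arm, counting women who meet the elimination criterion.

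Where questions about tingling or site reactions could reveal the group to the outcome recorder, the researcher who applies the electrodes can log them, on the same form in both arms.

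The cost is protocol wording, a few form lines, about 15 more minutes of symptom recording and a few questions per woman. Over the planned 58 women that is 58 × 15 = 870 minutes, or 14.5 hours. The recorder and the 24-hour contact already exist, and nothing in treatment changes.

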This study is designed as a randomized, controlled clinical study, with the first affiliated Hospital of Xi'an Jiaotong University as the research center. Participants undergoing singleton cesarean section under intraspinal anesthesia are recruited from November 1, 2021 to March 1, 2022. The diagnostic indicators of hypotension in this study are intraoperative systolic blood pressure $< 90\text{mmHg}$ or blood pressure decreased by more than 30% of basal blood pressure, the main outcome measures are the incidence of hypotension during 30 minutes after subarachnoid administration, and the secondary indicators are the specific changes of hemodynamic indexes, the usage of ephedrine, the incidence of nausea and vomiting, the incidence of dizziness, chest tightness and dyspnea during 30 minutes after subarachnoid administration, and fetal Apgar score. The patients are selected according to the inclusion and exclusion criteria, and the informed consent form are signed. First of all, the selected patients are numbered sequentially, and then the participants are randomly divided into control group and TEAS (transcutaneous acupoint electrical stimulation) group by SPSS software. In the TEAS group, 15 minutes before anesthesia at bilateral Neiguan points and Zusanli points begin to receive dense wave electrical stimulation with the frequency of 10/50Hz, and last until 30 minutes after subarachnoid administration. In the control group, 15 minutes is performed before anesthesia, and electrodes are connected at the same acupoint, but no electrical stimulation is given, the duration is the same as that of the TEAS group. During the trial, participants know which group they will be assigned to and which treatment they will receive. According to the grouping of random tables generated by SPSS, a researcher will independently give corresponding treatment measures to participants who has had signed the informed consent form, and cover up the screen of the electroacupuncture instrument. Another data collection researcher who does not know about the grouping records the vital signs and other complications of the participants. When the total number of cases reaches the minimum number of cases required by statistics or reaches the project case collection node (March 1, 2022), the data will be statistically analyzed and processed by professional statistical researchers.

Inclusion Criteria:

- 18 years \leq age < 55 years
- ASA classification I ~ II

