- full term ($37\text{ weeks} \leq \text{gestational weeks} < 42\text{ weeks}$)
- schedule for elective single cesarean section under spinal anesthesia
- no other clinical trial 3 months before the enrollment
- volunteer to participate and sign the informed consent form

Exclusion Criteria:

- severe preeclampsia or hypertension
- diabetes
- cardiac insufficiency
- mental abnormality or cognitive impairment or inability to communicate
- acupuncture points skin breakage, infection, allergy
- the researchers believe that there are any conditions that are not suitable for inclusion.

Elimination Criteria:

- be unwilling to continue the trial during the trial
- have adverse reactions caused by transcutaneous acupoint electrical stimulation during the trial
- the effect of intraspinal anesthesia is not good and drugs are added or intubation is changed to general anesthesia during the trial,
- intraspinal block level is too high above T4 or too low to below T10 during the trial
- loss of blood more than 400ml during the trial

2. Research methods

In this study, a randomized, controlled design method is used to study the pregnant women who meet the inclusion criteria of singleton cesarean section.

Sample size estimation:

Based on the pre-experimental results from July 5, 2021 to July 28, 2021, the incidence of hypotension is 40% in the TEAS group and 80% in the control group. The sample size and the incidence of hypotension in the TEAS group is compared with that in the control group are estimated by GPOWER3.1 software,. Using the z test of two independent samples in the non-parametric test, double tails, $\alpha=0.05$ 、 $1-\beta=0.85$ 、 $N2/N1=1$ 、 $P1=0.40$ 、 $P2=0.80$, 26 cases in each group are calculated. A total of 52 cases. According to the 10% lost follow-up rate, the minimum sample size in each group is 29 cases, with a total of 58 cases.

Random:

Randomized grouping is obtained by using SPSS software programming. First of all, the determined sample size is numbered from small to large according to the order of the operation, and then the number is inputted into the SPSS software. The random number is generated by the random number generator in the SPSS software program, and the generated random numbers are randomly grouped.

Control:

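### Does the 30% limb of the hypotension definition leave the primary endpoint open because it names no pressure component?

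*Protocol*

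**What the plan says.** The primary outcome in section 4 (Evaluation index, Main indicators) is "the incidence of hypotension during 30mintes after subarachnoid administration". The note that follows gives the definition: "definition of hypotension: intraoperative systolic blood pressure < 90mmHg or blood pressure decreased by more than 30% of basal blood pressure". The study summary at the start of the protocol uses the same two limbs, and its second limb is again "or blood pressure decreased by more than 30% of basal blood pressure".

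The baseline is set in section 3 (Research steps): "The blood pressure, heart rate and other hemodynamic parameters of the 5 minutes after the participants enter the room are recorded as basic values". After the spinal injection, "the hemodynamic data of the participants are recorded in 30 minutes every 2 minutes". The same event prompts treatment: "When hypotension occurs, ephedrine 5-10mg is given".

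The sample size in section 2 rests on pre-experimental results in which "the incidence of hypotension is 40% in the TEAS group and 80% in the control group".

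**The concern.** The word systolic qualifies the 90 mmHg limit and is not repeated for the 30% limb. The baseline is likewise described only as blood pressure. Read strictly, a woman could be counted as hypotensive on a fall in systolic, mean or diastolic pressure, and the three need not agree.

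Three consequences would follow if the gap were real in practice. The primary outcome could be scored in several ways, and picking among them after seeing the data would inflate the type I error. The pre-experimental rates of 80% and 40% might have been scored on a different component from the trial, which would weaken the sample size. Ephedrine use, a secondary outcome, is tied to the same word and would inherit the ambiguity.

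A side issue is that the absolute limb is described as intraoperative, while the outcome window opens at subarachnoid injection, before incision. A literal reader might ask whether early falls count.

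**Working it through.** **1. The plan's own figure.** Inputs from section 2: rates 0.40 and 0.80, two-sided alpha 0.05, power 0.85, equal groups. For a pooled z test with mean rate 0.60:

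n = [1.960 × √(2 × 0.60 × 0.40) + 1.036 × √(0.40 × 0.60 + 0.80 × 0.20)]² / 0.40²
= [1.358 + 0.655]² / 0.16 = 25.3, rounded up to 26 per group.

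With 10% loss: 26 / 0.90 = 28.9, rounded up to 29. Both stated figures reproduce.

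**2. What the 30% limb does if it is systolic.** A fall of more than 30% means a reading below 0.70 × baseline. This adds to the 90 mmHg limb only if 0.70 × baseline > 90, that is, baseline > 90/0.70 = 128.6 mmHg. From 120 the threshold is 84, and from 128 it is 89.6; both are already below 90. From 140 it is 98, where the relative limb does the work. The two limbs are complementary, and the relative limb serves women who start higher.

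**3. Whether the component can matter.** Assume a baseline of 120/75 mmHg, with mean pressure = diastolic + (systolic − diastolic)/3, so 90. The protocol gives no such values.

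| Reading | Systolic fall | Mean fall | Diastolic fall | Event (systolic / mean / diastolic) |
|---|---|---|---|---|
| 92/48 (mean 62.7) | 28/120 = 23.3% | 27.3/90 = 30.4% | 27/75 = 36.0% | no / yes / yes |
| 95/50 (mean 65.0) | 25/120 = 20.8% | 25/90 = 27.8% | 25/75 = 33.3% | no / no / yes |

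So the component can change who is an event. By how much cannot be computed from the protocol, which reports neither pressures nor incidence by component.

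**4. The multiplicity figure.** Assume baseline systolic pressure 120 (SD 12); mean maximal falls of 26% systolic, 29% mean and 32% diastolic (SD 9 points); correlation 0.5 to 0.85; no treatment effect; 29 per group; 20,000 simulated trials. Incidence is about 58% on systolic, 64 to 69% on mean and 70 to 75% on diastolic pressure. Each single scoring keeps the type I error below 5%. Choosing the best of three gives about 9 to 11%. If diastolic is left out and mean pressure is derived from the other two, choosing the best of two gives about 6.6 to 7.2%. On systolic scoring the 30% limb itself moves the incidence only from about 55% to 58%.

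These inputs are not calibrated to this trial: 58% on systolic is far from the 80% control rate in section 2. The model also ignores rescue, although section 3 has hypotension treated when it occurs, which alters later readings.

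**5. What the text itself supports.** The relative limb follows the absolute limb in one clause, and the second mention of blood pressure most naturally repeats the first. The list of monitored variables in section 3 names blood pressure, ECG, oxygen saturation and cardiac-output indices; mean and diastolic pressure appear nowhere. The summary and the section 4 note agree with each other. Section 3 has hypotension recorded over the 30 minutes, and section 2 (Open) assigns that recording to a researcher unaware of the grouping. No step is described in which the outcome is re-scored later on another component.

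**6. The side issue.** The summary puts the definition and the 30-minute window from subarachnoid injection in the same sentence, and section 4 repeats the window. Dropping readings before incision would contradict that stated window. Nor is there a conflict between outcome and rescue trigger, because one definition serves both.

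**The case for a change.** The strongest case for a change is that this is the protocol's own primary endpoint definition, which should not rest on inference when one word would settle it. Recording by someone unaware of the grouping limits measurement bias, but it does not fix the component, and nothing says that the statistical researchers are masked. The protocol also does not say how the pre-experimental rates were scored. If the control incidence under the trial's scoring were 60% instead of 80%, with the risk ratio held at 0.5, power at 26 per group would be about 0.59 against 0.86 as planned.

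Part of this stands. The qualifier is missing, and writing it in would cost nothing. The power argument is weaker: with the odds ratio held at 6, a control incidence of 60% gives power of 0.86, so the loss depends on which effect measure is assumed constant. It also supposes that the pre-experiment and the trial were scored differently, for which the protocol gives no sign. The multiplicity argument supposes selective reporting, not a planned analysis.

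**Conclusion.** No change to the plan is called for. The relative limb lacks a qualifier that a sensible analyst would supply from the same clause. Read as systolic, the endpoint is well defined: two limbs, a baseline from the first 5 minutes in the room, readings every 2 minutes, and a 30-minute window from subarachnoid injection. On that reading the 30% limb matters only above a baseline systolic pressure of 128.6 mmHg, and the primary test keeps its nominal level.

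The type I error of about 9 to 11% is conditional on conduct the protocol does not describe and on pressures, falls and correlations it does not give. The sample size arithmetic is unaffected.

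This conclusion assumes that systolic is what the sponsor means and that the pre-experimental rates were scored in the same way. Both are the ordinary reading, though neither is written down. It concerns endpoint scoring only and takes no view on which pressure component is clinically preferable.
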